8. SUBJECT SAFETY MONITORING

- Subject monitoring will be conducted by the Principal investigator, [name], Ph.D.
- All patients will be monitored at each visit for their participation for signs of discomfort or desire to discontinue the protocol. Specifically, they are in constant view of the research staff during the experiment. They are instructed to wave at the (non-recording) camera or else to call the researcher if they wish to stop the experiment. The researcher is within earshot of the participant at all times. The participants will also be explicitly told during the consenting procedure as well as after the sample shock procedure that it is their right to discontinue the study at any time.
- **Criteria for Withdrawal:** If a patient experiences clinically significant worsening, displays any suicidal ideation or active plans of suicide, reports adverse reactions to the experiment at any point during the study, appears to be in distress at any point during the procedures, or demonstrates adverse responses by way of the post-experimental assessment of adverse events, the patient will meet with [name] or [name], or their clinical staff, who will assess the patient's suitability for continuation in the study and will administer appropriate psychiatric treatment. If the psychiatrist determines that continuation is clinically counter-indicated, the patient will be removed from the protocol but will receive treatment at the NIH under the care of [name] or [name] until appropriate, long-term psychiatric care is arranged. The reasons for patients' discontinuation from the study will be logged and changes to procedures necessary to prevent future adverse reactions will be made.
- **Role of Medical Doctors:** The medical advisory investigator for this study, [name], will serve as the primary treating psychiatrist for anxiety patients enrolled in this protocol. Dr.

[name]'s role will include serving as the intervening psychiatrist in the event of adverse reactions or symptom worsening as well as delivering short-term treatment (1-2 months, not to exceed 3 months) to anxiety patients upon their completion of the protocol. Additionally, [name] will complete the initial psychiatric evaluation (described below) and will be on call for subjects along with other psychiatrists on the child anxiety on-call schedule to allow 24-7 on call coverage for patients in this protocol. In the event that participating patients experience symptom worsening while off-campus, they will call the child anxiety on-call schedule. When [name] is the on call-physician, he will provide the psychiatric treatment for this patient. Otherwise, the on-call physician at the time the patient calls will intervene and provide the necessary care. [name] and his associates in his program will serve as the primary treating psychiatrists for depressed patients in this protocol. [name] or a clinician in his group will be the primary treating physicians. They will intervene in the event of adverse reactions or symptom worsening and will as deliver appropriate treatment.

- **Healthy Controls:** Throughout experimental procedures, psychiatrically healthy subjects will be monitored by both a non-recording video camera and by a two-way audio telecom. Procedures will be stopped for any subject who asks to stop any procedure at any point. Subjects will be asked if they wish to continue with other phases of the study. Procedures will also be stopped for any subject who exhibits signs of distress during any phase of the study. At this point, subjects will be interviewed to confirm that they are in fact in distress and psychiatric intervention will follow when necessary. Subjects will be asked if they wish to continue with other phases of the study.
- **Psychiatric Patients:** Mood patients accepted into this protocol will have been thoroughly screened and assessed for inclusion/exclusion criteria by clinicians of the Experimental Therapeutics & Pathophysiology Branch of NIMH. For English speaking bipolar depressed patients, [name] and his team will be responsible for screening evaluations, the experiments and clinical assessments during each visit.
 - Monitoring during the experimental sessions is conducted by a research assistant under the supervision of a physician from this branch. Like healthy controls, patients will be monitored via non-recording camera and two-way audio telecom throughout experimental procedures.
 - All patients with anxiety psychiatric disorders will be provided with [name] pager number as well as other phone numbers for emergency psychiatric coverage, 24-hours/day. Patients with mood disorders will be provided with [name] or one of his physician's pager number as well as other phone numbers for emergency psychiatric coverage, 24-hours/day.
 - Patients will be monitored by way of multiple clinical assessments. The clinical assessments by the psychiatrist addresses not only the primary (mood) diagnosis, but also any allowed comorbid conditions with which the patient suffers. Symptom severity of both the primary and comorbid conditions is monitored and interventions provided by medical staff as deemed medically necessary

Below is a table delineating all scheduled clinical assessments for patients during each visit.

Schedule of Clinical Assessments for Patients*			
Session**	Time	Type of Assessment	Clinical Staff
1	upon arrival	Initial psychiatric evaluation	[name]
	upon arrival	SCID	credential staff clinician
	upon arrival	Assessment of symptom severity(C-MARS)	credential staff clinician
	end of session	Assessment of adverse reactions	[name]
2	upon arrival	Assessment of symptom severity(C-MARS)	credential staff clinician
	end of session	Assessment of adverse reactions	[name]
3	upon arrival	Assessment of symptom severity(C-MARS)	credential staff clinician
	end of session	Post-exp. psychiatric assessment	[name]

* Only includes scheduled assessments and does not include assessments/interventions to be administered in the case of adverse events.
**1 week interval between visits.

- **Initial Psychiatric Evaluation:** At the outset of screening, patients will meet with [name] or [name] for an initial psychiatric assessment. During this evaluation, the psychiatrists will assess the patients' suitability for this study based on the patient's psychiatric/medical history as well as the patient's current symptom profile. Patients participating in studies 1 and 2 will be informed that the study is not designed to treat their psychiatric disorder/s and that their condition may worsen while participating in this study. Additionally, patients will be reminded that psychopharmacologic and psychotherapeutic treatment options for anxiety and mood disorders are available in clinical practice outside of the NIH and delaying such treatment may have adverse effects on their mental health.
- **Study Phase:** If, during the course of the study, a subject's condition deteriorates to the point where emergency treatment is needed, the subject will be removed from the protocol. At this point or any other point where subjects are removed from the study for non-emergent reasons, clinical care will be provided by staff, under the direction of Drs. [name] or [name]. This care will continue until the case has been successfully stabilized, through the use of standard clinical practice in the treatment of anxiety and mood disorders. If patients require in-patient care, they will be hospitalized in one of the NIMH inpatient units.

- **Clinical Care After Treatment:** Following the completion of the study, psychiatric patient participants in the anxiety protocol will receive short term psychiatric treatment lasting 1-2 months (not to exceed 3 months) under the care of Drs. [name] and the adult anxiety program staff. The total amount of time that out-of-study care will be provided is expected to vary, given the diverse clinical needs of patients. Ideally, the team will provide care for between one and two months in most cases. However, efforts to transition care to the community will intensify after two months and the study team will make every effort to ensure that no more than 3 months of treatment are provided. Similarly, the depressed patients will receive care as outlined above under the direction of [name] and the mood disorders program staff. The time line of care as detailed above will be followed for these patients as well.

9. OUTCOME MEASURES

- a. Primary outcome measures: Primarily, we are interested in exploring the affective, cognitive and behavioral of our study's dependent measures. The primary outcome measures will be the startle reflex and performance on cognitive tasks.
- b. Secondary outcome measures: These measures include psychophysiological measures other than startle (e.g., skin conductance) and state and trait questionnaires.

10. STASTISTICAL ANALYSIS

The overall target N for the protocol is 663 healthy controls and 608 patients. Participants who drop out will be replaced. Participants may participate in more than one sub-study.

- Sub-study 1
 - **Analysis of data/study outcomes:** Startle amplitude during the verbal threat procedure will be averaged over cue and no cue (ITI) periods within conditions. There will be separate analyses for anxiety disorders and mood disorders. The data will be submitted to a Group (GAD, SAD, panic disorder, control or MDD, bipolar, control) x Condition (P, N, U) x Cue (cue, ITI) ANOVA. If this interaction is significant, within-group simple-effects comparing startle amplitudes during the ITI of predictable versus unpredictable conditions will be compared for all groups separately. Larger startle magnitudes in the unpredictable versus predictable condition suggest heightened sensitivity to unpredictability. Between group contrasts will also be computed to compare difference scores (i.e., differences between startle magnitudes during unpredictable and predictable conditions) across groups. In our pilot and published studies, we obtained the lowest effect size ($f=0.30$) for contextual fear (anxiety-potentiated startle).

- **Power analysis:** We set power at .80 and experiment-wise, two-tailed alpha at 0.05. Based on these parameters, we will need 18 subjects per group. Assuming a 15 % unusable data rate due to lack of startle response or equipment failure, approximately 22 subjects per group will be recruited for a total of 110 patients and 44 healthy controls.
- Sub-study 2
 - **Analysis of data/study outcomes:** Startle amplitude will be averaged over conditions (safe, threat) and WM load (View, 1, 2, 3). There will be separate analyses for anxiety disorders and mood disorders. The data will be submitted to a Group (GAD, SAD, panic, controls or MDD, bipolar, controls) x condition (safe, threat) x WM load (1-back, 2-back, 3-back).
 - **Power analysis:** Based on our published study in healthy controls (Vytal et al, in press), where we found a 2-way interaction between condition and WM load with an effect size of $\eta^2=0.20$, we estimate that we will need 20 subjects per group. Given a rate of 15% of unusable data, approximately 23 subjects per group will be recruited for a total of approximately 115 patients and 46 healthy controls. We will also need approximately 40 healthy controls to pilot various versions of the tasks for a total of 86 controls.
- Sub-study 3
 - **Analysis of data/study outcomes:** patients will be tested twice, before and after the 8-week treatment, while controls will be also tested twice, 8 weeks apart. Startle amplitude and performance will be averaged over conditions (safe, threat) and WM load (view, 1, 2, 3 for startle and 1, 2, 3 for performance). These data will be submitted to omnibus Group (patients, controls) x condition (safe, threat) x WM load (view, 1-back, 2-back, 3-back for startle and 1-back, 2-back, 3-back for performance) x Time (first session, second session) ANOVAs. However, the analysis will focus on the 3-back condition, where greater group differences are expected. Changes in fear-potentiated startle and differential performance (threat minus safe) in the 3-back condition from session 1 to session 2 will be compared between the two groups. Secondary measures will be subjected to multiple-regression analyses. For all such analyses, questionnaire scores will serve as predictor variables and different experimental outcomes will serve as dependent variables. Analyses will regress questionnaire scores dependent measures of interest: 1) anxiety-potentiated scores, 2) WM scores, and 3) attentional-bias scores. In so doing, we will be able to assess the combined and unique contributions of questionnaire scores to the variability in dependent measures.
 - **Power analysis:** We estimate that we will need 30 subjects per group. Given a rate of 25% of unusable data or non-completers, approximately 38 controls and 38 patients will be recruited.

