Another objective was to study the processes that separate fear and anxiety. While fear is a phasic response associated with an identifiable source that is thought to predict occurrence of an aversive stimulus, anxiety is a more persistent feeling of apprehensive anticipation of future danger (Barlow, 1988). We have demonstrated that the characteristics of these two forms of aversive responses – cued fear and generalized anxiety - could be modeled by administering predictable and unpredictable aversive events (shocks), respectively (Grillon, 2002; Grillon & Davis, 1997). Fear is operationally defined as an increase in startle amplitude during a threat cue that predicts an aversive event (fear-potentiated startle). Anxiety is operationally defined as an increased in startle amplitude during long periods of unpredictable aversive events (anxiety-potentiated startle). One of the past objectives of this protocol was to examine far-potentiated startle and anxiety-potentiated startle in anxiety disorders. We have found that patients with panic disorder and PTSD, but not generalized anxiety disorder (GAD), showed elevated anxiety-potentiated startle (Grillon, et al., 2008; Grillon, et al., 2009). Given that the underlying neural mediators of fear and anxiety are partially distinct (amygdala versus bed nucleus of the stria terminalis) (Davis, Walker, Miles, & Grillon, 2010), these results provide clues to potential pathophysiological mechanisms and targets for treatment.

2- Current studies

We are currently pursuing this line of research to address new questions. As indicated above we found increased anxiety-potentiated startle in PTSD and panic disorder but not GAD. Failure to obtain increased anxiety-potentiated startle in GAD may have been due to the use of mildly aversive stimuli (e.g., airblasts). We are currently examining whether more potent aversive stimuli such as shocks will lead to elevated anxiety-potentiated startle in GAD. We are also examining the specificity of the heightened anxiety-potentiated startle in patients with various types of anxiety disorders (e.g., social anxiety disorder). We are also testing patients with major depression (MDD) and bipolar disorder (BP) of contradictory finding regarding fear-potentiated startle and more generally emotional responses to

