2. STUDY OBJECTIVES

- a. Objective 1: To examine fear-potentiated startle and anxiety-potentiated startle in mood and anxiety disorders. To what extent does heightened anxiety-potentiated startle cut across distinct anxiety disorders? Are fear-potentiated startle and anxiety-potentiated startle also elevated in mood disorders?
- b. Objective 2: To examine the interaction between induced-anxiety and WM as cognitive load increases. Does anxiety affect WM performance and is this effect dependent on cognitive load? Can patients with mood or anxiety disorder reduce their anxiety by being engaged in a WM task?

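### Sub-study 1 states an experiment-wise alpha of 0.05 that the analysis it describes does not deliver

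*Combined protocol and SAP*

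**What the plan says.** All the relevant text is in Section 10, Sub-study 1. The power paragraph fixes the error rate: "We set power at .80 and experiment-wise, two-tailed alpha at 0.05". The analysis paragraph says "There will be separate analyses for anxiety disorders and mood disorders": one ANOVA with four groups (GAD, SAD, panic disorder, control) and one with three (MDD, bipolar, control), each crossed with Condition and Cue.

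Follow-up comes in two parts. The first is explicitly conditional: "If this interaction is significant, within-group simple-effects comparing startle amplitudes during the ITI of predictable versus unpredictable conditions" are examined in every group. The second is introduced without repeating that condition: "Between group contrasts will also be computed to compare difference scores". The number of contrasts is not given. Neither a division of alpha between the two ANOVAs nor a multiplicity procedure is mentioned.

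One power statement covers both analyses: "approximately 22 subjects per group will be recruited for a total of 110 patients and 44 healthy controls".

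**The concern.** Experiment-wise is a claim about a whole family of tests, and the described family is larger than one test at 0.05. What is at stake is how a single positive diagnosis would be read. Objective 1 in Section 2 asks "To what extent does heightened anxiety-potentiated startle cut across distinct anxiety disorders", and the Introduction says the group is examining "whether more potent aversive stimuli such as shocks will lead to elevated anxiety-potentiated startle in GAD", after elevated responses were found in panic disorder and PTSD but not in GAD. A result in which some diagnoses differ from controls and others do not is therefore exactly what the sub-study is built to look for. It is also the situation in which an omnibus gate stops protecting the remaining comparisons. A lone positive contrast would carry a stated 5% protection that the plan does not provide.

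**Working it through.** **Inputs from Section 10.** Two-sided alpha 0.05; two ANOVAs with 4 and 3 groups; 18 evaluable participants per group; 15% unusable data. The number of contrasts follows from the groups: 3 + 2 = 5 if each patient group is compared with controls, 6 + 3 = 9 if all pairs are compared.

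**The plan's own totals.** 18 / 0.85 = 21.2, rounded up to 22 per group. 5 × 22 = 110 patients and 2 × 22 = 44 controls. These reproduce, and 44 is consistent with one control group per ANOVA.

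**Step 1: the sub-study is the experiment.** Two independent omnibus tests at 0.05 give 1 − 0.95² = 1 − 0.9025 = 0.0975. If all 36 evaluable controls (2 × 18) serve both ANOVAs, simulation gives 9.4%. This step does not depend on the contrasts.

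**Step 2: each ANOVA is its own experiment, contrasts gated.** The gate is the planned Group × Condition × Cue interaction, with (4 − 1) × 2 = 6 numerator and 4 × 17 × 2 = 136 denominator degrees of freedom in the anxiety analysis. The contrasts are pooled-error t tests (4 × 17 = 68 df, two-sided 0.05) on the unpredictable-minus-predictable ITI difference score. Assumptions: 18 per group, normal data, compound symmetry, 40,000 runs. One anxiety diagnosis is shifted in the unpredictable ITI cell by d standard deviations of the difference score. The d values are illustrative, since the documents give none for this contrast.

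| True state, anxiety analysis | Any false pair | Any false patient-versus-control contrast |
|---|---|---|
| No group differs | about 2% | about 2% |
| One diagnosis differs, d=0.6 | 4% | 3% |
| One diagnosis differs, d=1.0 | 8% | 6% |
| One diagnosis differs, d=1.5 | 12% | 9% |

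The rate climbs with d because the gate opens more often. At d=0.6 it opens in only about 21% of runs. Once it is always open, the ceiling is the ungated error among the three groups that do not differ: 12% over their three pairs, 9% over the two patient-versus-control contrasts.

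**Step 3: contrasts not gated, no group differs.** Same pooled-error contrasts, 18 per group, separate controls:

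| Scope | Patient versus control | All pairs |
|---|---|---|
| Anxiety analysis | 12% (three) | 20% (six) |
| Mood analysis | 9% (two) | 12% (three) |
| Both | 20% (five) | 30% (nine) |

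**The case against.** Four arguments favour the plan.

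First, the anxiety and mood analyses address different patients and different parts of Objective 1, and 44 controls fit one control group each. Treating each ANOVA as its own experiment is legitimate, and the 9.75% then falls away. That stands as a possible reading. Against it, Section 4d calls Sub-study 1 an experiment in the singular, and one alpha statement covers both analyses.

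Second, the contrasts sentence follows the conditional one and says they will also be computed, so it can naturally be read as sharing the condition. A reader might infer that 20% to 30% is the plan's actual error rate. The documents do not support that: it is the rate on the less favourable of two open readings.

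Third, a reader might infer that the sponsor has decided against adjustment. The text is silent. It names no procedure, but it does not exclude one. What can be said is that the stated property has no stated means.

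Fourth, Section 9 describes the interest with "we are interested in exploring the affective, cognitive and behavioral", and exploratory work need not control experiment-wise error. That stands, and it is why correction for multiplicity is not demanded here. It does not justify stating a control that the analysis lacks.

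**Conclusion.** The alpha statement is wrong as written for the analysis described; the consequence is minor. No complete reading holds 5% throughout. With the whole sub-study as the experiment, the omnibus tests alone reach about 9.75%. On the most favourable reading (separate experiments, gated contrasts), 5% holds when no group differs, and still holds at d=0.6 with one diagnosis differing. It is exceeded at d=1.0 and above, on the compound-symmetry assumption.

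Two further inferences are not supported. A reader might take the gated inflation to be near 10% already for moderate effects. That would follow from a gate built on the difference score itself, whereas the planned gate is the three-way interaction, which opens less often. A reader might also conclude that 18 per group is wrong or that power is inadequate. The documents do not give enough about the test and the within-subject correlation to show that, and the point does not depend on it.

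**What to change.** Make the alpha statement match the analysis, in one of two ways.

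- **Restate it.** Replace experiment-wise with two-sided 0.05 for each ANOVA. State whether the between-group contrasts are run only after a significant interaction, and say that they are not protected at an experiment-wise 5%. This takes a few sentences in Section 10, with no added participants and no loss of power.
- **Deliver it.** If experiment-wise control is intended, name the procedure and the tests it covers, for example Holm over the five patient-versus-control contrasts (first step 0.05 / 5 = 0.01). This costs power. With 18 versus 18, a contrast with 80% power unadjusted (d=0.96) falls to 57% if only that diagnosis differs, or 68% if all five do.

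Either is acceptable; the sponsor should choose and say which. Do not write a single detectable difference into the plan: it is d=0.96 with 18 versus 18 but d=0.82 if 36 controls are shared, and the documents do not say which applies.

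### Sub-study 1: the stated f, power and alpha do not by themselves give 18 per group; if f = 0.30 is a between-group effect on the startle difference score, power is about 42% to 53%, not 80%

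*Combined protocol and SAP*

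**What the plan says.** Section 10, Sub-study 1, plans a mixed ANOVA: "Group (GAD, SAD, panic disorder, control or MDD, bipolar, control) x Condition (P, N, U) x Cue (cue, ITI) ANOVA". It is run twice: "There will be separate analyses for anxiety disorders and mood disorders". The anxiety model therefore has four groups and the mood model three. If the interaction is significant, predictable and unpredictable periods are compared within each group. In addition, "Between group contrasts will also be computed to compare difference scores".

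The next sentence gives the only effect size: in the sponsor's own earlier work, "we obtained the lowest effect size ($f=0.30$) for contextual fear (anxiety-potentiated startle"). The power paragraph follows: "We set power at .80 and experiment-wise, two-tailed alpha at 0.05", and then "Based on these parameters, we will need 18 subjects per group". Allowing for 15% unusable data, the plan recruits about 22 per group, or 110 patients and 44 controls.

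Section 2, Objective 1, asks: "To what extent does heightened anxiety-potentiated startle cut across distinct anxiety disorders"? It also asks whether the two startle measures are raised in mood disorders. Section 9 makes the startle reflex a primary outcome.

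**The concern.** Section 1 defines anxiety-potentiated startle as an increase in startle amplitude, so each subject contributes one difference score. Objective 1 can be answered only by comparing that score between patients and controls. The f = 0.30 is attached to this measure and comes straight after the between-group contrasts, and the sample size is stated per group. A reader will take the 80% to cover those contrasts. A one-score-per-subject comparison involves no repeated-measures correlation, and at f = 0.30 it needs far more than 18 per group.

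What is at stake is how a null result is read. Section 1 reports that patients with generalized anxiety disorder did not show the elevation before, suggests that the stimuli may have been too mild, and says that shocks are now being tried. A second null would be weighed against a claimed 80% power that the group contrast may not have.

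**Working it through.** **Inputs.** From Section 10, Sub-study 1: f = 0.30, power 0.80, two-tailed alpha 0.05, n = 18 usable per group, k = 4 or 3 groups, 15% unusable. Not given: the test that the 80% refers to, whether f is a between-group, within-subject or interaction effect, and any correlation between repeated startle measures.

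**1. The part that reproduces.** 18 / 0.85 = 21.2, rounded up to 22. Then 5 × 22 = 110 patients and 2 × 22 = 44 controls. The inflation and the totals are right.

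**2. Between-group comparison of one difference score per subject.** Noncentral F with λ = N f², where N = 18k, on k − 1 and N − k degrees of freedom. For two equal groups d = 2f = 0.60.

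| Comparison | λ at n = 18 | Power at n = 18 | n per group for 0.80 | f for 0.80 at n = 18 |
|---|---|---|---|---|
| Four groups (anxiety model) | 72 × 0.09 = 6.48 | 0.527 | 32 | 0.40 |
| Three groups (mood model) | 54 × 0.09 = 4.86 | 0.468 | 37 | 0.44 |
| One patient-control contrast | 36 × 0.09 = 3.24 | 0.417 | 45 | 0.48 (d = 0.96) |

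**3. Where 17 to 19 can come from.** Every correlation ρ in this step is an assumption. With m repeated measures and sphericity, the usual formulas are λ = f² N m / (1 − ρ) for a Group × Condition interaction and λ = f² N m / (1 + (m − 1)ρ) for a group effect averaged over conditions. Numbers needed per group at f = 0.30:

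- Interaction, two levels (predictable, unpredictable): at ρ = 0, 19 for three groups and 17 for four; at ρ = 0.1, 18 for three groups. For two groups, 19 at ρ = 0.2 and 17 at ρ = 0.3. At ρ = 0.5, only 10 (three groups) or 9 (four groups), so that 18 per group would have power 0.977 or 0.992.
- Group effect averaged over three conditions: 18 for three groups at ρ = 0.2 and 18 for four groups at ρ = 0.3. At ρ = 0.5 these become 25 and 22.
- Within one group, paired test at dz = 0.60: 24 needed, power 0.67 at 18.
- Within one group over three conditions, ρ = 0.5: 20 needed, power 0.765 at 18.

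On these formulas the required number runs from about 9 to 25 at ρ = 0.5 alone, depending on the test.

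**4. What the interaction convention implies on the difference score.** With two levels, f on the difference score is f × √(2 / (1 − ρ)). At ρ = 0 this is 0.30 × √2 = 0.42; at ρ = 0.5 it is 0.30 × √4 = 0.60. Where that convention supports 18, it does so by assuming a larger effect than 0.30 on the score being compared.

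**5. Experiment-wise alpha.** The plan names no adjustment method. If a Bonferroni split over three or six pairwise contrasts is assumed, power at d = 0.60 and n = 18 falls from 0.417 to about 0.25 or 0.18.

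**The case against.** The plan never says that f = 0.30 is a between-group effect, and the studies it came from are not in the documents. Its lead test is a mixed-model interaction; the between-group contrasts are introduced as an addition, and the 80% is tied to no named test. Standard repeated-measures formulas reach 18, or close to it, under several modest correlations and not only at zero. Under others, 18 per group is more than enough. A reader might therefore infer from the 42% to 53% that 18 is simply an arithmetic error and that the sub-study is underpowered. The documents do not support that: both the size and the direction of any discrepancy depend on a definition of f that they do not give.

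That part of the objection stands, and the shortfall has to be stated conditionally. It does not restore the 80% claim. The plan says that 18 follows from f, power and alpha, and it does not. Some routes to 18 also test something else: the group effect averaged over conditions concerns overall startle level, and the within-group tests do not compare patients with controls. If the 80% belongs to one of those, the comparison that answers Objective 1 has no stated power.

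**Conclusion.** The power statement cannot be reproduced from its stated inputs, and as written the 80% cannot be claimed for the between-group difference-score comparisons. If f = 0.30 is a between-group effect on that score, power at 18 usable per group is about 0.53, 0.47 and 0.42 (four groups, three groups, one unadjusted contrast). This assumes equal groups, normal errors with common variance, and no split of alpha.

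The detectable effects do not depend on how f = 0.30 was defined: with 18 per group, 80% power on the difference score requires f of about 0.40 (anxiety model), f of about 0.44 (mood model) or d of about 0.96 for a single unadjusted contrast, and more if alpha is split. This limits what a null contrast can show. It is not evidence that the enrolment target must rise.

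**What to change.** In Section 10, Sub-study 1:

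- Name the test, the type of f and any assumed correlation that produced 18.
- Replace the general 80% claim, as far as it covers the between-group comparisons, with wording such as: *With 18 usable subjects per group, the between-group comparison of difference scores has 80% power for f of about 0.40 in the four-group anxiety model, f of about 0.44 in the three-group mood model, and d of about 0.96 for one unadjusted patient-control contrast; the detectable effect is larger if alpha is divided among contrasts.*
- Add, if it applies: *If f = 0.30 is a between-group effect on the difference score, power is about 0.42 to 0.53, and a null group contrast will not be read as excluding an effect of that size.*

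The cost is a few sentences and a less favourable stated power. Enrolment, design and the planned analyses are unchanged.
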